#### 4.5. Sample Size

This is the first study of TMB-001 using the VIIS index. No formal power calculations were performed to establish sample size since there were no VIIS response data available. A sample size of 45 subjects (15 per treatment group) has been selected to provide initial data on VIIS response and to enable formal sample size calculations for future studies, as well as to assist in dose selection for Phase 3 study.

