### 5.2. Randomization and Subject Identification Code

Subjects who meet all inclusion criteria and no exclusion criteria will be randomized to a treatment group in a 1:1:1 ratio, stratified by CI subtype.

All subjects will be centrally assigned to randomized study treatment using an Interactive Web Response System (IWRS). Before the study is initiated, the log in information and directions for the IWRS will be provided to each study center.

Study medication use will be accounted and dispensed at the study visits as summarized in the Schedule of Activities (Section 1.2 of the protocol).

Subjects will be assigned a randomization number formatted, Rsnn where s is an indicator for the CI subtype (1 = ARCI-LI, 2 = RXLI) and nn is the random permutation of 01 - 45.

The listings for inclusion in an appendix to the clinical study report will be prepared after the study has been unblinded.

In the listings, subjects will be identified by subject number (assigned at randomization), with treatment as a secondary grouping identifier. Screening number will be shown only on the listing of informed consent data and screen failure data.

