### 9.2.2. Secondary Efficacy Endpoints

- The proportion of subjects achieving IGA treatment success will be the key secondary endpoint. The IGA score will be dichotomized to “treatment success” or

“treatment failure” where “treatment success” is defined as at least a 2-grade decrease in severity score relative to Baseline. Active treatment will be compared with vehicle at Visit 6 (EOS) using the CMH test stratified by CI subtype and 95% confidence intervals will be calculated for the difference in proportions for the treatment groups.

Other Secondary Endpoints:

- The time to achieve VIIS-50 ( $\geq 50\%$  reduction in VIIS scaling score for body sites that had a Baseline score  $\geq 3$ ) that is maintained at the next observation. If VIIS-50 is first achieved at Visit 6 (EOS), then the endpoint is considered to have been met. A time to event analysis will be performed using the Kaplan-Meier (K-M) method and log rank test to compare active treatment with vehicle. The results from K-M analysis will be tabulated as well as graphically presented.
- Changes in VIIS scaling score relative to Baseline at Visit 4 and Visit 5:  
The treatment groups will be compared with respect to the change from Baseline using mixed model of repeated measures (MMRM) including terms for treatment, visit, treatment by visit interaction, and the Baseline VIIS scaling score serving as the covariate. VIIS scaling score is defined as the average score of grades for all body areas assessed at that visit. From the model, the active to vehicle treatment differences will be estimated. Additionally, two-sided confidence intervals will be provided.
- Proportion of subjects with IGA “treatment success” at Visit 4, Visit 5, and Visit 6 (EOS):  
Descriptive statistics (including frequencies and percentages) for IGA success rate will be presented by treatment group for each CI subtype and overall. Success is defined as a  $\geq 2$ -point reduction in IGA score from Baseline.
- Proportion of subjects with IGA score representing “cleared” or “almost cleared” at Visit 6 (EOS):  
Descriptive statistics (including frequencies and percentages) for IGA scores representing “cleared” or “almost cleared” will be presented by treatment group for each CI subtype and overall. “Cleared” or “Almost cleared” is defined as an IGA score of 0 or 1.
- Changes in percent BSA relative to Baseline with CI in the Treatment/Assessment Areas at Visit 3, Visit 4, Visit 5, and Visit 6 (EOS):  

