Descriptive statistics (including mean, median, SD, min, and max) for observed and change from Baseline values in percent BSA at each visit will be presented by treatment group for each CI subtype and overall.
- Change from Baseline in Itch-Numeric Rating Scale (I-NRS) score at Visit 6 (EOS):  
The treatment groups will be compared with respect to the change from Baseline using mixed model of repeated measures (MMRM) including terms for treatment, visit, treatment by visit interaction, and the Baseline I-NRS value serving as the covariate. From the model, the active to vehicle treatment differences will be estimated. Additionally, two-sided confidence intervals will be provided.

- Change in DLQI from Baseline to Visit 6 (EOS):  
Descriptive statistics (including mean, median, SD, min, and max) for observed and change from Baseline values in DLQI and CDLQI at each visit will be presented by treatment group for each CI subtype and overall.

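### Percent BSA, DLQI/CDLQI and IGA 0/1 are named secondary efficacy endpoints, but SAP 9.2.2 plans no active-minus-vehicle difference or confidence interval for them

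*SAP*

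**What the plan says.** SAP 4.6.1.3 and Protocol Table 1 list change in percent BSA, change in DLQI and an IGA score of 0 or 1 at Visit 6 among the other secondary efficacy endpoints. SAP 9.2.2 then gives their analyses:

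- IGA 0/1: "Descriptive statistics (including frequencies and percentages) for IGA scores representing" clear or almost clear, by arm, by CI subtype and overall.
- Percent BSA: "Descriptive statistics (including mean, median, SD, min, and max) for observed and change from Baseline values in percent BSA at each visit", again by arm.
- DLQI: observed and change from Baseline "values in DLQI and CDLQI at each visit will be presented by treatment group".

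SAP 9.1.4 and 9.1.5 and Protocol 9.4.1.2 say the same for DLQI and BSA. SAP Appendix 2 lists summary tables for all three and no CMH, MMRM or other between-group table for them.

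Other endpoints in the same section are treated differently. For IGA success of at least two grades, the stratified CMH test is accompanied by this: "95% confidence intervals will be calculated for the difference in proportions for the treatment groups". VIIS and I-NRS change get an MMRM with the Baseline value as covariate, from which active-to-vehicle differences and two-sided intervals are reported.

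On size, SAP 4.5 states: "No formal power calculations were performed to establish sample size since there were no VIIS response data available". The total is 45, with 15 per arm.

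**The concern.** The trial is vehicle-controlled and its efficacy objective concerns two concentrations, so the quantity of interest for each efficacy endpoint is a dose-minus-vehicle difference. For these three the plan stops at three columns, which readers will compare by eye without a stated estimate or precision. The SAP gives no reason for the split. It also runs against the endpoint ranking: some exploratory endpoints in SAP 9.2.3 get a log-rank test or a pooled-active MMRM, while these named secondary endpoints get no contrast.

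For percent BSA and DLQI/CDLQI, part of any chance Baseline imbalance also stays in the unadjusted change. Randomisation is stratified only by CI subtype, and Protocol 5.1 admits affected BSA from 10% to 90%, so Baseline BSA can differ appreciably between arms of 15.

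**Working it through.** **1. Planned between-arm analysis, endpoint by endpoint**

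| Endpoint | Planned contrast |
|---|---|
| VIIS-50, Visit 6 (primary) | stratified CMH, 95% CI |
| IGA 2-grade success, Visit 6 (key secondary) | stratified CMH, 95% CI |
| I-NRS success, Visit 6 | CMH, 95% CI (SAP 9.1.3) |
| VIIS change, I-NRS change | MMRM differences, two-sided CI |
| Time to VIIS-50 | log-rank |
| Percent BSA change | none |
| DLQI/CDLQI change | none |
| IGA 0/1, Visit 6 | none |
| IGA 2-grade success, Visits 4 and 5 | none |

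The sentence in Protocol 9.4.1.2 that compares success rates does not rescue IGA 0/1, because it defines IGA success as a reduction of at least 2 points.

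**2. Inputs.** 15 per arm (SAP 4.5; 3 × 15 = 45 agrees with the stated total) and a 95% level (SAP 9.2.2). The documents give no SD, Baseline-to-follow-up correlation r or response rate, so these are assumed below. There is no plan figure for these endpoints to reproduce.

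**3. Precision of a mean difference, 15 v 15**, in units of the outcome SD, with equal Baseline and follow-up variances:

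- Unadjusted follow-up value: t(0.975, 28) × √(2/15) = 0.75.
- Change from Baseline: multiply by √(2(1−r)).
- Baseline-adjusted: t(0.975, 27) × √(2/15) × √(1−r²).

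| r (assumed) | change score | adjusted |
|---|---|---|
| 0.3 | ±0.89 | ±0.72 |
| 0.5 | ±0.75 | ±0.65 |
| 0.7 | ±0.58 | ±0.54 |

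With 12 per arm the adjusted figures become ±0.81, ±0.74 and ±0.61.

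**4. Variance ratio, adjusted to change score:** (1−r²) / (2(1−r)) = (1+r)/2. This gives 0.75 at r = 0.5, 0.90 at 0.8 and 0.95 at 0.9. The square roots are 0.866, 0.949 and 0.975, so intervals are about 13%, 5% and 2.5% narrower. The ratio ignores the small cost of estimating the slope and does not apply to IGA 0/1.

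**5. How much Baseline imbalance remains in raw change.** With equal variances the share is (1−r). As an illustration, assume Baseline BSA uniform from 10% to 90%: SD = 80/√12 = 23.1 points, and the standard error of a 15 v 15 Baseline difference = 23.1 × √(2/15) = 8.4 points. An imbalance of one standard error then shifts the change contrast by (1−0.5) × 8.4 = 4.2 points at r = 0.5, and by (1−0.8) × 8.4 = 1.7 points at r = 0.8.

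**6. Precision for IGA 0/1, 15 v 15, assumed counts.** Wald half-width = 1.96 × √(p₁(1−p₁)/15 + p₂(1−p₂)/15).

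| Active v vehicle | difference | Newcombe 95% CI | Wald half-width |
|---|---|---|---|
| 3/15 v 1/15 | 0.13 | −0.13 to 0.39 | 0.24 |
| 5/15 v 1/15 | 0.27 | −0.03 to 0.52 | 0.27 |
| 6/15 v 2/15 | 0.27 | −0.05 to 0.53 | 0.30 |
| 9/15 v 3/15 | 0.40 | 0.05 to 0.64 | 0.32 |

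**The case against.** The strongest defence is that the split is deliberate. The protocol synopsis, Protocol 9.4.1.2 and the SAP agree that DLQI and BSA are descriptive. The trial is openly unpowered, and describing lower-tier endpoints in 45 subjects is a defensible choice. That stands as an argument against formal tests. It does not argue against estimates with intervals, which an early-phase trial can report without claiming significance.

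IGA 0/1 also overlaps an endpoint that already has a contrast. From a Baseline IGA of 3, reaching 0 or 1 is the same event as a 2-grade decrease; from 4 it is a subset. This weakens the case for IGA 0/1. It does not remove it, because 0/1 is listed as its own endpoint and the listed inclusion criteria set no Baseline IGA.

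A reader might also infer four stronger things, which the documents do not support:

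- That only raw values are reported. The SAP summarises change from Baseline for BSA and DLQI/CDLQI.
- That the trial can yield no estimate. Arm n, mean and SD give an unadjusted difference and interval, and IGA 0/1 counts by arm and subtype give a stratified one. A Baseline-adjusted contrast cannot be rebuilt from those tables.
- That Baseline imbalance passes whole into the change scores. Only the (1−r) share does.
- That dose selection or Phase 3 planning rests on these endpoints. SAP 4.5 says "A sample size of 45 subjects (15 per treatment group) has been selected to provide initial data on VIIS" response and mentions dose selection in general, without tying it to BSA, DLQI or IGA 0/1.

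**Conclusion.** The point holds as an inexpensive improvement: no dose-v-vehicle difference or interval is pre-specified for percent BSA, DLQI/CDLQI or IGA 0/1, although suitable methods stand in the same section and the Baseline BSA and DLQI values are collected (Protocol 8.2.4 and 8.2.5). It does not affect the primary or key secondary analysis.

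The variance ratio in step 4 measures the gain from adjustment, not the size of the omission. It rests on an assumed r and equal variances, and the gain shrinks as r rises. The added intervals will be wide, so they will show how little 15 per arm can settle on these endpoints. That is useful information, and columns of means do not display it.

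**What to change.** In SAP 9.2.2:

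- **Percent BSA:** analyse change in the Treatment Area with the MMRM already written for VIIS, with Baseline percent BSA as covariate. Report each dose-minus-vehicle difference at Visit 6 with its 95% CI. Keep the VIIS Assessment Area and earlier visits as supportive.
- **DLQI and CDLQI:** these are different instruments with different severity bands and separate tables, so fit separate models for change at Visit 6, each adjusted for its own Baseline score, with 95% CIs. Keep CDLQI descriptive if too few children are enrolled, and state the minimum number in advance.
- **IGA 0/1 at Visit 6:** use the same subtype-stratified CMH test and difference in proportions with 95% CI as for IGA success.

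Label all of these as nominal and not multiplicity-controlled. IGA success at Visits 4 and 5 is also descriptive only and could be handled in the same way or left as it is.

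The cost is SAP wording, added columns in Tables 14.2.2.5, 14.2.4.1, 14.2.5.1 and 14.2.5.2, and an entry in SAP section 11, which now reports no change from the protocol. Limiting BSA to one area and one visit keeps the count down: 4 outcomes × 2 doses = 8 intervals per population, or 16 over ITT and PP. Intervals for BSA at all four visits in both areas would make it (2 × 4 × 2) + 6 = 22 per population, or 44. Sample size, visits and data collection are unchanged.

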### 9.2.3. Exploratory Endpoints

- Time to 2 or more points decrease from baseline in IGA:  
A time to event analysis will be performed using the Kaplan-Meier (K-M) method and log rank test to describe the time to 2 or more points decrease from baseline in IGA.
- Time to achieve a score of 0 for both IGA and VIIS scaling:  
A time to event analysis will be performed using the Kaplan-Meier (K-M) method and log rank test to describe the time to achieve a score of 0 for both IGA and VIIS scaling.
- Time to achieve a score of 1 for both IGA and VIIS scaling:  
A time to event analysis will be performed using the Kaplan-Meier (K-M) method and log rank test to describe the time to achieve a score of 1 for both IGA and VIIS scaling.
- Kappa agreement analysis for VIIS and IGA scores at each visit:  
Kappa coefficients will be calculated for VIIS scaling and IGA score agreement at each visit.
- Spearman and Pearson Correlation coefficient will be calculated between VIIS scaling scores and IGA scores, and between VIIS target sites scores and IGA at each visit.
- Proportion of subjects with VIIS treatment success by body region:  
If data allows, proportion of subjects with VIIS treatment success will be compared between treatment groups in cases where the same body areas have been treated. Descriptive statistics (including frequencies and percentages) VIIS treatment success will be presented by body region.
- Proportion of subjects with VIIS treatment success by genetic mutation:  
Descriptive statistics (including frequencies and percentages) for VIIS treatment success will be presented by genetic mutation.
- Proportion of subjects with IGA treatment success by genetic mutation:  
Descriptive statistics (including frequencies and percentages) for IGA treatment success will be presented by genetic mutation.
- Proportion of subjects with VIIS treatment success by phenotype:  
Descriptive statistics (including frequencies and percentages) for VIIS treatment success will be presented by phenotype.
- Proportion of subjects with IGA treatment success by phenotype:

Descriptive statistics (including frequencies and percentages) for IGA treatment success will be presented by phenotype.

- Proportion of subjects with VIIS treatment success by drug/BSA ratio:  
Drug/BSA ratio will be calculated for each participant and values will be flagged according to median ratio as above or below median. Descriptive statistics (including frequencies and percentages) for VIIS treatment success will be presented by drug/BSA ratio.
- Proportion of subjects with IGA treatment success by drug/BSA ratio:  
Drug/BSA ratio will be calculated for each participant and values will be flagged according to median ratio as above or below median. Descriptive statistics (including frequencies and percentages) for IGA treatment success will be presented by drug/BSA ratio.
- Proportion of subjects with VIIS treatment success by drug/BMI ratio:  
Drug/ BMI ratio will be calculated for each participant and values will be flagged according to median ratio as above or below median. Descriptive statistics (including frequencies and percentages) for VIIS treatment success will be presented by drug/ BMI ratio.
- Proportion of subjects with IGA treatment success by drug/BMI ratio:  
Drug/ BMI ratio will be calculated for each participant and values will be flagged according to median ratio as above or below median. Descriptive statistics (including frequencies and percentages) for IGA treatment success will be presented by drug/ BMI ratio.
- Proportion of subjects with VIIS treatment success by drug/kg ratio:  
Drug/ kg ratio will be calculated for each participant and values will be flagged according to median ratio as above or below median. Descriptive statistics (including frequencies and percentages) for VIIS treatment success will be presented by drug/ kg ratio.
- Proportion of subjects with IGA treatment success by drug/kg ratio:  
Drug/ kg ratio will be calculated for each participant and values will be flagged according to median ratio as above or below median. Descriptive statistics (including frequencies and percentages) for IGA treatment success will be presented by drug/ kg ratio.
- Proportion of subjects with VIIS treatment success based on BSA Stratification:  
Participants will be stratified according to Baseline BSA data. Descriptive statistics (including frequencies and percentages) of VIIS treatment success will be presented by BSA stratification.
- Proportion of subjects with IGA treatment success based on BSA Stratification:  
Participants will be stratified according to Baseline BSA data. Descriptive statistics (including frequencies and percentages) of VIIS treatment success will be presented by BSA stratification.

- Proportion of subjects with VIIS treatment success by OTC steroid cream usage: Descriptive statistics (including frequencies and percentages) for VIIS treatment success will be presented by OTC steroid cream.
- Proportion of subjects with IGA treatment success by OTC steroid cream usage: Descriptive statistics (including frequencies and percentages) for IGA treatment success will be presented by OTC steroid cream.
- Proportion of subjects with VIIS treatment success by assessment medium: Descriptive statistics (including frequencies and percentages) for VIIS treatment success will be presented by assessment medium (online vs onsite).
- Proportion of subjects with IGA treatment success by assessment medium: Descriptive statistics (including frequencies and percentages) for IGA treatment success will be presented by assessment medium (online vs onsite).
- Proportion of subjects with VIIS treatment success by drug interruption: If data allows, descriptive statistics (including frequencies and percentages) for VIIS treatment success will be presented by the following drug interruption categories: frequency, duration, location and action outcome of the drug interruption.
- Proportion of subjects with IGA treatment success by drug interruption: If data allows, descriptive statistics (including frequencies and percentages) for IGA treatment success will be presented by the following drug interruption categories: frequency, duration, location and action outcome of the drug interruption.
- Proportion of subjects who meet both the primary and major secondary endpoint: Descriptive statistics (including frequencies and percentages) of subjects who meet both the primary and major secondary endpoint.
- Proportion of subjects who meet VIIS 75 scaling at visit 6: Descriptive statistics (including frequencies and percentages) of subjects who meet VIIS 75 ( $\geq 75\%$  reduction in VIIS scaling score for VIIS target body sites that had a Baseline score  $\geq 3$ ) at visit 6.
- Proportion of subjects with VIIS "treatment success" (VIIS-50) at non-target body sites:  
In cases where VIIS body areas have been identified as non-target sites, and had a baseline score of  $\geq 3$ , the proportion of subjects at Visit 6 (EOS) relative to Baseline with 50% or greater decrease in sum of VIIS scaling score in non-target sites will be presented using frequency statistics.
- Changes from Baseline in VIIS score, Active Vs Vehicle  
Active treatment groups will be combined into one group and compared to vehicle group with respect to the change from Baseline using mixed model of repeated measures (MMRM) including terms for treatment, visit, treatment by visit interaction, and the Baseline VIIS value serving as the covariate.
- Changes from Baseline in I-NRS score, Active Vs Vehicle

Active treatment groups will be combined into one group and compared to vehicle group with respect to the change from Baseline using mixed model of repeated measures (MMRM) including terms for treatment, visit, treatment by visit interaction, and the Baseline I-NRS value serving as the covariate.

## 10. PHARMACOKINETIC/PHARMACODYNAMIC DATA

Pharmacokinetic/Pharmacodynamic parameters will not be evaluated in this study.

## 11. CHANGES FROM THE ANALYSIS PLANNED IN THE PROTOCOL

There are no changes from the planned analysis described in the protocol.

## 12. DATA LISTINGS AND SUMMARY TABLES

### 12.1. Interim/Preliminary Data Analysis

No interim analyses are planned.

### 12.2. Listings and Tables for Clinical Study Report

The data listings and summary tables, and associated figures, planned to be generated from the study data are listed in Appendix 1 and Appendix 2, respectively. The numbering and titles may vary in the final presentation, depending on the amount of data to be presented.

Listings, tables and figures will be provided to the Sponsor in a form suitable for inclusion as appendices to the Clinical Study Report, in RTF or PDF format. The layout will be landscape A4 size, with a margin of 1 inch. The default font for listings and tables will be Courier New 8 pt.

In the summary tables other than those included in the main text of the report, special characters and formatting will not be used. For example, units will be shown as ug ( $\mu\text{g}$ ) and  $\text{m}^2$  ( $\text{m}^2$ ), if/where these example units are applicable.

Data in listings will be ordered by treatment, then subject, then date/time.

Data to be presented graphically includes: Visual Index for Ichthyosis Severity success rate, Time to VIIS-50 - Kaplan-Meier Analysis, Investigator's Global Assessment success rate and Itch- Numeric Rating Scale success rate. All of these efficacy endpoints will be graphically presented using both, ITT and PP population.

### 12.3. Data Transfer to the Study Sponsor

At the conclusion of the study, Avance will provide the Sponsor with an electronic copy of the listings, tables and graphs, along with analysis data sets in SAS transport format and XPT format. This may be provided by email or by upload, as determined by the Sponsor.

Details of the statistical analyses will be retained in the Avance study file for reference.

### **13. GENERAL CONSIDERATIONS FOR DATA MANAGEMENT AND ANALYSIS**

#### **13.1. Analysis Packages**

SAS 9.4 or higher (SAS Institute Inc., Cary, NC, USA) will be used for generating data listings and summary tables and associated figures, and for performing statistical analysis.

